10.3.5 Monitoring

The investigator will permit study-related monitoring, audits, and inspections by the IRB, the sponsor, and government regulatory agencies, of all study related documents (e.g. source documents, regulatory documents, data collection instruments, study data etc.). The investigator will ensure the capability for inspections of applicable study-related facilities (e.g. pharmacy, diagnostic laboratory, etc.).

Participation as an investigator in this study implies acceptance of potential inspection by government regulatory authorities and applicable compliance offices.

11. PARTICIPANT RIGHTS AND CONFIDENTIALITY

The study will employ standard methods for protecting the confidentiality of research materials through the use of coded identification numbers that are specific to the study on all materials except those that are necessary for participant contact, follow-up, and ongoing linkage with data such as those from medical records, using password-protected computer data files and databases, and locked file cabinets for storing hard copies of any other study materials. Only study personnel who need to track participants for follow-up purposes have access to the identifying information for individual study participants. No personally-identifiable information (protected health information) except the minimum necessary for study purposes are shared with co-investigators, and any sharing of data is by encrypted, password-protected data files. In addition to the procedures outlined above, confidentiality and privacy are further enhanced as each institution maintains research databases behind institution-specific password-protected firewalls.

ECG recordings will be uploaded and stored in a secured data platform, accessible only to permitted Mayo Study personnel; additionally, it will be uploaded into the patient's EPIC EMR.

No preliminary or final results will be released or published with identifying information or reported on an individual level, and all epidemiologic data will be presented as statistical summaries. No statistics will be published based on fewer than 5 subjects, a practice consistent with HIPAA and most confidentiality guidelines.

Information about study subjects will be kept confidential and managed according to the requirements of the Health Insurance Portability and Accountability Act of 1996 (HIPAA). Those regulations require a signed subject authorization informing the subject of the following:

- What protected health information (PHI) will be collected from subjects in this study
- Who will have access to that information and why
- Who will use or disclose that information
- The rights of a research subject to revoke their authorization for use of their PHI.

In the event that a subject revokes authorization to collect or use PHI, the investigator, by regulation, retains the ability to use all information collected prior to the revocation of subject authorization. For subjects that have revoked authorization to collect or use PHI, attempts should be made to obtain permission to collect at least vital status (long term survival status that the subject is alive) at the end of their scheduled study period.

11.1. Institutional Review Board (IRB) Review

11.2. Informed Consent Forms

A signed consent form will be obtained from each participant. The consent form will describe the purpose of

the study, the procedures to be followed, and the risks and benefits of participation. A copy will be given to each participant and this fact will be documented in the participant's record.

For patients not fluent in English, an interpreter will be present to translate the informed consent and for the discussion of the informed consent with the trained study team member. It is already a standard of care at Mayo Clinic that all patients considered not fluent enough in English will have interpreter services. Thus this study builds and extends on this practice.

11.3. Participant Confidentiality

The confidentiality of all participants will be maintained according to the Health Insurance Portability and Accountability Act (HIPAA), any special data security requirements, and record retention per the sponsor's requirements.

Any data, specimens, forms, reports, or records that leave the site will be identified only by a participant identification number (Participant ID, PID) to maintain confidentiality. All records will be kept in a locked file cabinet. All computer entry and networking programs will be done using PIDs only. Information will not be released without written permission of the participant, except as necessary for monitoring by IRB, the FDA, the NIA, and the OHRP.

11.4. Study Discontinuation

The study may be discontinued at any time by the IRB, the NIA, the OHRP, the FDA, or other government agencies as part of their duties to ensure that research participants are protected.

12. ETHICAL CONSIDERATIONS

This study is to be conducted according to United States government regulations and Institutional research policies and procedures.

This protocol and any amendments will be submitted to a properly constituted local Institutional Review Board (IRB), in agreement with local legal prescriptions, for formal approval of the study. The decision of the IRB concerning the conduct of the study will be made in writing to the sponsor-investigator before commencement of this study.

All subjects for this study will be provided a consent form describing this study and providing sufficient information for subjects to make an informed decision about their participation in this study. This consent form will be submitted with the protocol for review and approval by the IRB for the study. The formal consent of a subject, using the Approved IRB consent form, must be obtained before that subject undergoes any study procedure. The consent form must be signed by the subject himself and the individual obtaining the informed consent.

13. COMMITTEES

This study will not convene any particular committee such as a Steering Committee or an Executive Committee, a Publication Committee, or an Adjudication Committee.

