7. STUDY INTERVENTIONS

Interventions, Administration, and Duration

Patients will be randomized to either standard medical therapy or standard medical therapy + Smartheart home telemonitoring device. The device will be supplied by the "SHL" telemedicine for each patient in the intervention group for the period of 90 (+/-7) days from the randomization. Patients will be followed for 90 (+/-7) days. At randomization and at the end of the study period the patients will be asked to fill out quality of life questionnaire and return back the Smartheart device by mailing back the device in the padded box covered by

[figure not shown]

Figure 2. Call work-flow

insurance in case it is damaged upon receipt to Mayo Clinic. Medications during the study period will be prescribed by the treating physician, no change of medications will be performed by the study team.

The SmartHeart, developed by SHL Telemedicine Ltd., was approved by the FDA on 2012 (K113514). It is a personal, hand-held device, enabling an individual to immediately transmit a 12-lead ECG from anywhere and anytime, using a smart phone application, to a physician's office, hospital or monitoring center. The ECG output from Smartheart device was compared to standard 12 lead ECG recordings and was found to be reliable. Data will be labeled with a subject's medical record number and by date of transmission. The data will be uploaded from Smartheart device to the US cloud (located in USA), and sent by email directly to designated Mayo Clinic CICU NP/PA smartphone devices email address. The smartphone device will be carried by the NP/PA 24/7 and will give a loud alert for every incoming ECG. The ECG data will be uploaded and accessible in the patient's EPIC EMR.

The smart phone application will send push notifications to the patients to remind them to perform test ECG at Week 1, Week 2, and Week 4 (optional, if patient has not performed Week 2 ECG). Patients will also be notified every other day after Week 1, if not completed.

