9.2. Sample Size and Randomization

Patients will be randomized to either standard medical therapy or the medical therapy plus the Smartheart 12 lead ECG home device.

The primary combined endpoint parameter is the rate of ED visits/rehospitalizations as well as related downstream cardiovascular testing (echocardiogram, stress test or coronary CT, or invasive coronary angiogram) at 90 (+/-7) days after discharge and mortality rates during the 90 (+/-7) days of follow up. Based on the most recent in-house registry data, we have about 50 AMI patients undergoing PCI a month. Accordingly, we have at least 600 patients a year who are discharged with a diagnosis of AMI from Saint Mary's Hospital.

Our own registry data further indicate that 24% of revascularized AMI patients will present to the ED or will be readmitted within 90 days. This is in keeping with the published literature citing a rate of 20-30%. Half of these patients will present for cardiovascular complaints and may get further testing, including echocardiogram, stress test or coronary CT, or invasive coronary angiogram. Having a 12-lead ECG available and the phone triage available to direct care may impact not only emergency presentation but also downstream testing. This will be considered in this trial, and each of these will be considered as a component to the combined primary endpoint event. Assuming that patients presenting with cardiovascular concern may receive two of the outlined downstream test as they present to the ED and hospital, the estimated event rate will be 48%. With 120 patients in each arm the study we would be adequately powered (beta error <0.2) to show a statistically significant (at alpha error levels of <0.05) for a 37.5% event reduction.

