9.5. Outcome measures

9.5.1. Primary trial objective

The primary aim of the trial is to compare the cardiac ED visits and hospital readmission rates as well as downstream testing at 90 (+/-7) days after hospitalization for MI between group 1 and group 2.

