9.5.2.1. Outcome measures

- Rate of ED visit and rehospitalization, overall and related to cardiovascular and non-cardiovascular causes
- Rate of downstream testing modalities (echocardiogram, stress test or coronary CT, or invasive coronary angiogram)
- Rate of MACE as defined above
- Amount of money in US dollars that was spent for any medical service related to cardiovascular and non-cardiovascular diseases in both study groups.
- Quality of life questionnaire score in both study groups at the time of enrollment and at 90 days.

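### Cardiovascular cause of ED visits, readmissions and MACE hospitalizations is assigned in an open-label trial with no stated criteria, assessor or masking, so labels could differ by arm

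*Combined protocol and SAP*

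**What the plan says.** **Outcomes that need a cause.** Section 9.5.2.1 lists as a secondary outcome: "Rate of ED visit and rehospitalization, overall and related to cardiovascular and non-cardiovascular causes". Objective 3.2(a) makes the same split. MACE, defined in the Objectives row of Section 1, includes hospitalization for named cardiovascular reasons such as unstable angina, heart failure and arrhythmia.

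**Who assigns it, and how.** No section names the person who assigns cause or gives criteria for doing so. Section 13 closes one route: "This study will not convene any particular committee such as a Steering Committee or an Executive Committee, a Publication Committee, or an Adjudication Committee". Section 10.3.2 also declines a quality control committee.

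**Who knows the arm.** Under 8.1.2 the patient and the treating cardiologist are told the assignment. Under 10.3.1 the study staff who deal with patients also manage the forms and database. The Schedule of Evaluations collects ED visits, hospitalizations and MACE in a day-90 research call, at the time point when the device is returned. No masked assessor is described.

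**What the chart shows.** Section 7: "The ECG data will be uploaded and accessible in" the patient's EPIC record; Section 11 repeats this. Section 10.2 takes clinical data from medical records, and Section 5 adds retrospective follow-up of events.

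**The primary endpoint.** Section 9.5.1.1 counts ED visits, readmissions and the listed tests with no restriction by cause. Section 9.5.1, however, words the primary aim as to "compare the cardiac ED visits and hospital readmission rates as well as downstream testing".

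**The concern.** Whether a chest-pain visit is called cardiovascular is often a judgement. Here the information behind that judgement differs by arm by design. In group 2 a symptomatic episode may come with a home ECG, an NP/PA reading and a short history (Sections 4.2 and 5); the same episode in group 1 has none of these. Anyone who reads the chart to assign cause can see the tracings and so infer the arm.

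If labels depend on arm, the cardiovascular/non-cardiovascular comparison and the cause-specific part of MACE can show a difference when there is none, or hide one. The expected counts are small, so a handful of labels is enough to move the estimate.

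**Working it through.** **1. The plan's own figure.** Section 9.2 gives a combined endpoint rate of 48%, 120 per arm, and power above 80% at alpha 0.05 "for a 37.5% event reduction". Sidedness is not stated; I take two-sided. The device-arm rate is 0.48 x (1 - 0.375) = 0.30, and the mean rate is 0.39.

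Power = Phi{[0.18 x sqrt(120) - 1.96 x sqrt(2 x 0.39 x 0.61)] / sqrt(0.48 x 0.52 + 0.30 x 0.70)} = Phi{(1.972 - 1.352) / 0.678} = Phi(0.914) = 0.82.

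The stated power reproduces. Nothing below disputes it.

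**2. Expected cardiovascular presentations.** Section 9.2 gives 24% of patients with an ED visit or readmission by 90 days, half for cardiovascular complaints.

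- Any visit or readmission: 0.24 x 120 = 28.8 per arm.
- Cardiovascular: 28.8 / 2 = 14.4 per arm, or 12% of patients.

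**3. What a few labels do to the estimate.** One label is worth 1/14 = 7% of the arm's count. Suppose there is no true effect.

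- Four group 2 patients moved out of the cardiovascular category: 14 vs 10, an apparent reduction of 4/14 = 29%. Pooled rate 24/240 = 0.10; z = (4/120) / sqrt(0.10 x 0.90 x 2/120) = 0.0333 / 0.0387 = 0.86; p = 0.39.
- Four moved in: 14 vs 18, an apparent increase of 4/14 = 29%.
- In the first case the overall counts stay at 29 vs 29, while the non-cardiovascular counts become 15 vs 19. The shift is visible only if all three rates are shown together.

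**4. What it does to the false-positive rate.** Assume a true rate of 12% in both arms and that a share m of group 2's cardiovascular patients is labelled non-cardiovascular. Sum the product of the binomial probabilities Bin(x; 120, 0.12) and Bin(y; 120, 0.12(1 - m)) over all pairs where the uncorrected chi-square test rejects, that is |z| > 1.96 with z = (x - y)/120 / sqrt(2 x pbar x (1 - pbar)/120) and pbar = (x + y)/240.

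| m (assumed) | Expected in group 2 | Significant, favouring device | Significant, either direction |
|---|---|---|---|
| 0 | 14.4 | 2.5% | 5.0% |
| 10% | 13.0 | 4.8% | 6.0% |
| 20% | 11.5 | 8.7% | 9.3% |
| 30% | 10.1 | 15.1% | 15.4% |

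The documents give no value for m, and the table assumes one direction of relabelling. It shows sensitivity; it is not a forecast.

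**5. Which outcomes are exposed.**

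| Outcome | Needs a cause label? |
|---|---|
| ED visits/readmissions by cause (3.2(a), 9.5.2.1) | Yes |
| MACE hospitalizations (Section 1) | Yes |
| ED visits/readmissions overall (9.5.2.1) | No |
| Tests (3.2(b), 9.5.2.1) | No, counted by modality |
| Primary endpoint as defined in 9.5.1.1 | No |
| Primary aim as worded in 9.5.1 | Yes, for ED visits, if the word cardiac is applied |

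**The case against.** Leaving out an adjudication committee is defensible in a single-site study of 240 patients that calls itself a pilot and defines its primary endpoint without regard to cause. There are also partial safeguards: retrospective follow-up for consistency (Section 5), and computerized checks and source document verification (10.3.3). That stands as an argument against demanding a committee. It does not answer the point, because none of these measures masks anyone or says what counts as cardiovascular.

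A reader might infer more than the documents support:

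- **That unblinded study staff decide cause.** This is plausible from 8.1.2, the Schedule of Evaluations and 10.3.1, but no section says so. Treating-team diagnoses might simply be transcribed. The gap is the silence.
- **That tests are exposed in the same way.** They are counted by type. Only the word related in 3.1 and 9.2 leaves room for judgement.
- **That the primary result is biased.** Under 9.5.1.1 a visit relabelled non-cardiovascular still counts.
- **That the shift favours the device.** A reassuring home ECG could pull a label toward non-cardiovascular. But under 4.2, patients with reassuring findings are advised to postpone care and those with a true event to seek it, so group 2 patients who reach the ED may carry an abnormal tracing, which pulls the other way. Moreover, the documents say the ECGs are filed in EPIC; they do not say that the triage assessment is.
- **That mislabelling could imitate the design effect.** The 37.5% in 9.2 applies to the 48% combined endpoint, not to the 12% cardiovascular subset, so the two should not be compared.

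**Conclusion.** The point holds for secondary outcomes. The cardiovascular/non-cardiovascular split of ED visits and readmissions, and the cause-specific MACE hospitalizations, depend on a label for which the plan gives no criteria, no named assessor and no masking, in an open-label trial whose device tracings sit in the chart. Labels could differ by arm; direction and size are unknown.

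With about 14 such patients expected per arm, the main risk is to the estimate. The rise in false-positive probability from 2.5% to about 5-15% rests on the assumed 10-30% relabelling, on relabelling in one direction, and on a true rate of 12% in both arms.

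The primary endpoint of 9.5.1.1 is outside the problem unless the narrower wording of 9.5.1 governs. The change is worth making because it is cheap, not because the trial's main conclusion is in danger.

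**What to change.** 1. In 9.5.2.1, state that cause for ED visits, readmissions and MACE hospitalizations is assigned from the treating facility's principal discharge diagnosis, against a code list fixed before any outcome extract is made. A list chosen afterwards would give no protection.
2. Have missing or ambiguous cases classified by an existing team member who takes no triage calls, from an extract without arm, SmartHeart tracings or triage notes.
3. Report overall, cardiovascular and non-cardiovascular rates side by side by arm, so that movement between categories can be seen.
4. Reconcile 9.5.1 with 9.5.1.1 on whether the primary endpoint is limited to cardiac ED visits. If it is, rules 1 and 2 must cover it too.

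The cost is a code list and a data-extract specification. No committee is needed, so Section 13 can stand, and the sample size and the 82% power do not change. The downside is some coding error and residual bias: the treating cardiologist knows the arm and clinicians at the site can open the same record, so the coded diagnosis may itself be influenced. Coding error cannot be assumed equal in the two arms.

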14. PUBLICATION OF RESEARCH FINDINGS

Publication of the results of this trial will be governed by the policies and procedures developed by the Steering Committee. Any presentation, abstract, or manuscript will be made available for review by the sponsor and the NIA prior to submission.

APPENDIX A

DATA AND SAFETY MONITORING PLAN

Table 1. Enrollment by Month of Study

Month	# Expected	# Screened	# Enrolled or Randomized	# Withdrawn	# Actual (# Enrolled - # Withdrawn)	# Cumulative (Sum of # Actual by Month)
1						
2						
3						

Table 2. Demographics

Characteristics	N	N%
Gender		
Female		
Male		
Age		
Mean (SE)		
Median (min, max)		
<34 years		
34-44 years		
45-54 years		
55-64 years		
65-74 years		
75-84 years		
>84 years		
Ethnicity		
Hispanic or Latino		
Not Hispanic or Latino		
Unknown		
Race		
AIAN		
Asian		
Nat Hawaiian/Other Pac Islander		
Black or African American		
White		
Other		
More than one race		
Unknown		

Table 3. Subject Status

Pt Identifier	Date Enrolled	Date Completed Study	Study Status	Reason for Withdrawal	% Adherence to Intervention	Intervention Duration (Weeks)
Subj001						
Subj002						
Subj003						

Status:

A = Active

C = Completed

W = Withdrawn

L = Lost to follow-up

% Compliance to Intervention: $(\# \text{ tablets taken}/\text{total } \# \text{ per protocol}) * 100$

or

 $(\# \text{ classes taken}/\text{total } \# \text{ of sessions should have attended}$

per protocol) * 100

Table 5. Frequency of Specific Symptoms

Symptoms	AE Code (MedRA, CTCAE)	N%
Fatigue		
Dyspnea		
Palpitations		
(Pre-)Syncope		
Chest pain		

Table 7. Subject Deaths

Pt Identifier	DOB	Date Enrolled	Treatment Date	Cause of Death	Date of Death	Comments
Subj001						
Subj002						
Subj003						

APPENDIX B

DSMP SAMPLE STUDY REPORT OUTLINE

Study Report Outline

- I. Table of Contents
- II. Introduction
 - A. Summary of Study Status and Issues or Problems
 - B. Report Preparation Procedures
- III. Study Description
 - A. Project Organization Chart, Personnel
 - B. Brief Statement of Purpose of Trial
 - C. Projected Timetable and Schedule
 - D. List of Any Resource Centers
- IV. Study Administration
 - A. Recruitment Status
 - i. Enrollment by Year/Month
 - ii. Comparison of Targeted to Actual Enrollment
 - B. Retention Status
 - i. Overall Subject Status
 - ii. Individual Subject Status
- V. Study Data Reports/Tables or Figures
 - A. General Information
 - i. Enrollment (see Appendix B, Table 1)
 - ii. Demographic/Baseline Data (see Appendix B, Table 2)
 - iii. Subject Status (see Appendix B, Table 3)
 - B. Safety Assessment
 - i. Treatment Duration for All Subjects (see Appendix B, Table 3)
 - ii. AE Data
 - a. Overall Listing (see Appendix B, Table 4)
 - b. Specific Symptom Listing (see Appendix B, Table 5)
 - c. SAE Listing (see Appendix B, Table 6)
 - d. Subject Deaths (see Appendix B, Table 7)
